#### **Prior/Concurrent Clinical Study Experience**

26. Has received an investigational agent or has used an investigational device within 4 weeks prior to intervention administration.

#### **Other Exclusions**

- 27. Has a "superscan" bone scan. This is defined as an intense symmetric activity in the bones and diminished renal parenchymal activity on screening bone scan such that the presence of additional metastases in the future could not be evaluated.
- 28. Has not adequately recovered from major surgery or has ongoing surgical complications.

## 5.3 Lifestyle Considerations

## 5.3.1 Meals and Dietary Restrictions

Participants are required to fast 2 hours predose and 1 hour postdose.

Foods that are CYP3A inhibitors must not be consumed during the study. Grapefruit and star fruit are known to be CYP3A inhibitors, and should not be consumed for 2 weeks before the first dose of MK-1088 and for the entire duration of the study. Consumption of CYP3A4 inhibitors, such as grapefruit juice, may significantly increase the levels of MK-1088 and cause increased toxicity. St. John's Wort is a CYP3A inducer, and the consumption of St. John's Wort or products containing St. John's Wort may reduce the levels of MK-1088. A partial list of examples of CYP3A inhibitors is provided in Section 6.5.

#### 5.3.2 Caffeine, Alcohol, and Tobacco Restrictions

No restrictions are required.

## 5.3.3 Activity Restrictions

Patients should avoid prolonged exposure to sun.

#### 5.4 Screen Failures

Screen failures are defined as participants who consent to participate in the clinical study, but are not subsequently entered in the study. A minimal set of screen-failure information is required to ensure transparent reporting of screen-failure participants to meet the CONSORT publishing requirements and to respond to queries from regulatory authorities. Minimal information includes demography, screen-failure details, eligibility criteria, and any AEs or SAEs meeting reporting requirements as outlined in the data entry guidelines.

Participants who fail screening may be rescreened for eligibility after consultation between the investigator and the Sponsor and written documentation of the collaborative decision on participant management.

#### 5.5 Participant Replacement Strategy

To adequately evaluate the safety of the doses administered in this study, all participants enrolled must meet the criteria for evaluability for Cycle 1. Participants are considered nonevaluable and will be replaced if:

- They are allocated, but not treated.
- They discontinue from the study without the occurrence of a DLT, before completing all the safety evaluations for reasons other than treatment-related AEs.

• They receive less than 75% of the total MK-1088 (or pembrolizumab infusion, if appropriate) in Cycle 1 (eg, if the infusion had to be discontinued due to an infusion reaction) and did not experience a DLT.

Participants who are not evaluable will be replaced unless accrual to the cohort has stopped. Nonevaluable participants will not be counted toward the total number of participants in the cohort for DLT evaluation.

If a participant experiences a DLT in Cycle 1, study intervention may be discontinued after discussion between the Sponsor and investigator. However, if the participant is deriving clinical benefit from the study intervention, the participant may be allowed to continue after discussion between the Sponsor and the investigator.

#### 6 STUDY INTERVENTION

Study intervention is defined as any investigational intervention(s), marketed product(s), placebo, or medical device(s) intended to be administered to a study participant according to the study protocol.

Clinical supplies (study intervention[s]) provided by the Sponsor will be packaged to support enrollment and replacement participants as required. When a replacement participant is required, the Sponsor or designee needs to be contacted before dosing the replacement participant. Clinical supplies will be affixed with a clinical label in accordance with regulatory requirements.

## 6.1 Study Intervention(s) Administered

The study intervention(s) to be used in this study are outlined in Table 5.

Table 5 Study Interventions

Arm Name	Arm Type	Inter- vention Name	Inter- vention Type	Dose Formulation	Unit Dose Strength(s)	Planned Dosage Level(s)	Route of Adminis- tration	Regimen/ Treatment Period	Use	IMP/ NIMP	Sourcing
Part 1: Arm 1 and Arm 2	Experi mental	MK-1088	Drug	Tablet	50 mg, 100 mg	DL1: 100 mg DL2: 200 mg DL3: 400 mg DL4: 600 mg DL5: 800 mg	Oral	Day 1 to Day 21 of each treatment cycle for up to 35 cycles; QD dosing	Experi mental	IMP	Provided centrally by the Sponsor
Part 1: Arm 2	Experi mental	Pembro- lizumab (MK-3475)	Drug	Solution for Infusion	100 mg per Vial	200 mg	IV Infusion	Day 1 of each treatment cycle for up to 35 cycles; Q3W dosing	Experi mental	IMP	Provided centrally by the Sponsor
Part 2: (To be speci- fied)	Experi mental	MK-1088	Drug	Tablet	50 mg 100 mg	Will be based on the RP2D from Part 1	Oral	Day 1 to Day 21 of each treatment cycle for up to 35 cycles; QD dosing	Experi mental	IMP	Provided centrally by the Sponsor
Part 2: (To be speci- fied)	Experi mental	Pembro- lizumab (MK-3475)	Drug	Solution for Infusion	100 mg per Vial	200 mg	IV Infusion	Day 1 of each treatment cycle for up to 35 cycles; Q3W dosing	Experi mental	IMP	Provided centrally by the Sponsor

DL=dose level; EEA=European Economic Area; IMP=investigational medicinal product; IV=intravenous; NIMP=noninvestigational medicinal product; QD=once daily; Q3W=every 3 weeks; RP2D=recommended Phase 2 dose.

The classification of IMP and NIMP in this table is based on guidance issued by the European Commission and applies to countries in the EEA. Country differences with respect to the definition/classification of IMP/NIMP may exist. In these circumstances, local legislation is followed.

Part 2 Arm Names will be specified in an amendment once the RP2D is determined in Part 1.

All supplies indicated in Table 5 will be provided per the "Sourcing" column depending on local country operational requirements. If local sourcing, every attempt should be made to source these supplies from a single lot/batch number where possible (eg, not applicable in the case where multiple lots or batches may be required due to the length of the study, etc).

Refer to Section 8.1.8 for details regarding administration of the study intervention.

Throughout the study, the first intake of MK-1088 will occur at the trial site on Day 1 of each cycle for Arm 1 and Arm 2 (shortly before the pembrolizumab infusion in Arm 2). MK-1088 will be administered orally, once daily. While in the clinic setting, pembrolizumab will be administered through an IV infusion as described in the Pharmacy Manual. Subsequent dosing of MK-1088 will be administered once daily QD by the participant (ie, unsupervised at their home) at approximately the same time each day, until Day 1 of the next cycle. For the MK-1088 dose on Day 2 of Cycles 1 and 2, the participant should refrain from MK-1088 administration until required study procedures on this day (eg, blood draw for MK-1088 PK assay) have been completed.

#### **6.1.1** Medical Devices

Not applicable.

## 6.2 Preparation/Handling/Storage/Accountability

## **6.2.1** Dose Preparation

Details on preparation and administration of MK-1088 (and pembrolizumab) are provided in the appropriate Pharmacy/Procedures Manual.

Concomitant chemotherapeutic/immunotherapeutic agents will be prepared and administered per the approved product label(s).

## 6.2.2 Handling, Storage, and Accountability

The investigator or designee must confirm appropriate temperature conditions have been maintained during transit for all study intervention received, and any discrepancies are reported and resolved before use of the study intervention.

Only participants enrolled in the study may receive study intervention, and only authorized site staff may supply or administer study intervention. All study interventions must be stored in a secure, environmentally controlled, and monitored (manual or automated) area in accordance with the labeled storage conditions with access limited to the investigator and authorized site staff.

The investigator, institution, or the head of the medical institution (where applicable) is responsible for study intervention accountability, reconciliation, and record maintenance (ie, receipt, reconciliation, and final disposition records).

For all study sites, the local country Sponsor personnel or designee will provide appropriate documentation that must be completed for drug accountability and return, or local discard and destruction if appropriate. Where local discard and destruction is appropriate, the investigator is responsible for ensuring that a local discard/destruction procedure is documented.

The study site is responsible for recording the lot number, manufacturer, and expiry date for any locally purchased product (if applicable) as per local guidelines unless otherwise instructed by the Sponsor.

The investigator shall take responsibility for and shall take all steps to maintain appropriate records and ensure appropriate supply, storage, handling, distribution, and usage of study interventions in accordance with the protocol and any applicable laws and regulations.

## 6.3 Measures to Minimize Bias: Randomization and Blinding

# **6.3.1** Intervention Assignment

Intervention allocation will occur centrally using an IVRS. There are 2 intervention arms. Participants will be allocated to 1 of 2 intervention arms: MK-1088 monotherapy (Arm 1) or MK-1088 in combination with pembrolizumab (Arm 2) using an IVRS in Part 1.

Participants will be allocated centrally through IVRS. Arm 1 monotherapy slots will be filled first to generate monotherapy safety data before enrolling participants at that dose in Arm 2. After Arm 2 combination therapy has opened, slots in Arm 1 at a higher MK-1088 dose than Arm 2, if available, will be allocated first before Arm 2 slots are assigned. If both arms are open at the same dose of MK-1088, then assignment to Arm 1 or Arm 2 will be alternated.

In Part 1 of the study, intervention will be allocated by nonrandom assignment. Enrollment into the MK-1088 in combination with pembrolizumab combination intervention arm (Arm 2) may begin once all participants complete 1 cycle of MK-1088 monotherapy (Arm 1) at DL1, complete the DLT evaluation period, and a dose-escalation decision to the next dose level has been made. This ensures that the starting dose of MK-1088 in the combination arm will be at least one dose level below that being tested concurrently in the MK-1088 monotherapy arm. If both Arm 1 and Arm 2 are open for enrollment at different doses Arm 1 will be allocated first. If, according to the adjusted mTPI algorithm, a dose de-escalation is recommended in Arm 1 (MK-1088 monotherapy) resulting in both monotherapy and combination arms open at the same dose, IVRS will alternate participant assignment between Arm 1 and 2 starting with Arm 1. For example, if the guidance of the adjusted mTPI indicates a dose de-escalation to the prior dose level of 200 mg after at least 3 DLT-evaluable participants at the 400 mg dose cohort of Arm 1 (MK-1088 monotherapy) have completed Cycle 1 and the 200 mg dose cohort of Arm 2 (MK-1088 in combination with pembrolizumab) is enrolling, then both arms are open for enrollment at the same dose. In that situation, the first participant will be allocated to Arm 1, the second participant will be allocated to Arm 2, the third participant will be allocated to Arm 1, etc. An observation period of at least 24 hours will occur between intervention initiation in participants enrolled within each dose level. Each new dose cohort will open for enrollment without delay once

the 21-day DLT observation period of the previous dose cohort is completed and a dose-escalation decision is made.

When Part 2 is open for enrollment, IVRS will allocate participants by tumor type.

#### 6.3.2 Stratification

No stratification based on age, sex, or other characteristics will be used in this study.

## 6.3.3 Blinding

This is an open-label study; therefore, the Sponsor, investigator, and participant will know the intervention administered.

## **6.4** Study Intervention Compliance

If there are interruptions in the study intervention schedule or infusion/injection was stopped, the details of and reason for any interruption or infusion/injection cessation of study intervention will be documented in the participant's medical record.

- When participants self-administer study intervention(s) at home, compliance with study intervention will be assessed at each visit. Compliance will be assessed by direct questioning and counting returned tablets during the site visits and documented in the source documents and CRF. Deviation(s) from the prescribed dosage regimen should be recorded in the CRF.
- A record of the number of MK-1088 tablets dispensed to and taken by each participant must be maintained and reconciled with study intervention and compliance records. Intervention start and stop dates, including dates for intervention delays and/or dose reductions will also be recorded in the CRF.

Refer to Section 6.6.1 for Dose Modification and Toxicity Management Guidelines for irAEs associated with pembrolizumab monotherapy, coformulations, or IO combinations and for other allowed dose interruptions.

## 6.5 Concomitant Therapy

Medications or vaccinations specifically prohibited in the exclusion criteria are not allowed during the ongoing study. If there is a clinical indication for any medication or vaccination specifically prohibited, discontinuation from study intervention may be required. The investigator is to discuss prohibited medication/vaccination with the Sponsor's Clinical Director. The final decision on any supportive therapy or vaccination rests with the investigator and/or the participant's primary physician. However, the decision to continue the participant on study intervention requires the mutual agreement of the investigator, the Sponsor, and the participant.

The following medications and vaccinations are prohibited during the study:

Antineoplastic systemic chemotherapy or biological therapy

59

- Participants with mCRPC should not remain on androgen receptor blockers such as enzalutamide, abiraterone, nilutamide, etc. Participants are allowed to remain on GnRH/ LHRH agents after progression as part of standard of care (as allowed by local regulations).
- Immunotherapy not specified in this protocol
- Chemotherapy not specified in this protocol
- Investigational agents other than pembrolizumab
- Radiation therapy

Note: Radiation therapy to a symptomatic solitary lesion or to the brain may be allowed at the investigator's discretion after the DLT observation period for the participant to be considered evaluable for DLT.

• Live or live-attenuated vaccines within 30 days before the first dose of study intervention and while participating in the study.

Note: Any licensed COVID-19 vaccine (including for Emergency Use) in a particular country is allowed in the study as long as they are mRNA vaccines, adenoviral vaccines, or inactivated vaccines. These vaccines will be treated just as any other concomitant therapy.

Investigational vaccines (ie, those not licensed or approved for Emergency Use) are not allowed.

- Systemic glucocorticoids except when used for the following purposes:
  - To modulate symptoms of an AE that is suspected to have an immunologic etiology
  - For the prevention of emesis
  - To premedicate for IV contrast allergies
  - To treat COPD exacerbations (only short-term oral or IV use in doses >10 mg/day prednisone equivalent)
  - For chronic systemic replacement not to exceed 10 mg/day prednisone equivalent
- Other glucocorticoid use except when used for the following purposes:
  - For topical use or ocular use
  - Intraarticular joint use
  - For inhalation in the management of asthma or COPD

## H2 Blockers or PPI

The participant must not take H2 blockers or PPI during the trial from 5 days before the start of the study treatment to 5 days after the last administration of MK-1088. The investigator should use their medical judgment when a participant presents with an H2 blocker or PPI treatment or call the Sponsor Clinical Director for clarification.

Of note, antacids, such as calcium carbonate or aluminum hydroxide-based product, will be allowed during the study, and are recommended to be taken either 4 hours before or after dosing of MK-1088.

• Strong/moderate inhibitors/inducers/substrates of the CYP3A4 enzymes.

Investigators should check an actively updated list of drugs that are clinically relevant substrates, inducers or inhibitors of cytochrome P450, including CYP3A4 (http://medicine.iupui.edu/clinpharm/ddis/table.asp) as well as the product labeling of these compounds for reference.

CYP3A4 inhibitors/inducers/substrates are listed below. The participant must not take the treatments listed in Table 6 during the trial after the start of the study treatment. Since this list is not comprehensive, the investigator should use their medical judgment when a participant presents with a medication not on the list or call the Sponsor Clinical Director for clarification.

Table 6 Examples of Medications, Supplements, and Other Substances Prohibited During the Trial

Strong 3A4	Strong CYP3A4	Moderate CYP3A4	CYP3A4 Substrates With Narrow
Inducers a,d	Inhibitors b,d	Inhibitors b,d	Therapeutic Range c,d
carbamazepine phenobarbital phenytoin rifabutin rifampin troglitazone	indinavir nelfinavir ritonavir clarithromycin itraconazole ketoconazole nefazodone atazanavir saquinavir telithromycin	amprenavir aprepitant diltiazem erythromycin fluconazole fosamprenavir verapamil grapefruit juice	alfentanil c ergotamine c diergotamine c cyclosporine c fentanyl c pimozide c quinidine c sirolimus c tacrolimus c astemizole c,e terfenadine c,e cisapride c,e paclitaxel c repaglinide c lurasidone c

Strong 3A4	Strong CYP3A4	Moderate CYP3A4	CYP3A4 Substrates With Narrow
Inducers a,d	Inhibitors b,d	Inhibitors b,d	Therapeutic Range c,d

Abbreviation: CYP = cytochrome P450.

- a Strong 3A4 inducers listed are those that decrease plasma AUC values of 3A4 substrates by 30% or higher.
- b Moderate inhibitors are defined as causing a ≥2- but <5-fold increase in the AUC values or 50-80% decrease in clearance of sensitive CYP3A substrates when the inhibitors were given at the highest approved dose and the shortest dosing interval in clinical evaluations. Strong inhibitors are defined as causing a ≥5-fold increase in the plasma AUC values or more than 80% decrease in clearance.
- CYP3A4 substrates with narrow therapeutic range refers to drugs whose exposure-response indicates that increases in their exposure levels by the concomitant use of CYP3A4 inhibitors may lead to serious safety concerns. For specific information, see the Classification of Substrates tables available at:
  - http://www.fda.gov/Drugs/DevelopmentApprovalProcess/DevelopmentResources/DrugInteractionsLabeling/ (then click "Drug Development and Drug Interactions: Table of Substrates, Inhibitors and Inducers")
- d Compiled from the in vivo inhibitors and inducers, inhibitor classification, and substrate classification tables available at:
  - http://www.fda.gov/Drugs/DevelopmentApprovalProcess/DevelopmentResources/DrugInteractionsLabeling/ (then click "Drug Development and Drug Interactions: Table of Substrates, Inhibitors and Inducers") and from the CYP450 drug interaction table (accessed June 2012) available at: http://medicine.iupui.edu/clinpharm/DDIs/table.aspx
- e Not available in the United States, and limited availability in the European Union.

If the investigator determines that a participant requires any of the aforementioned treatments for any reason, study intervention must be discontinued.

All treatments that the investigator considers necessary for a participant's welfare may be administered at the discretion of the investigator in keeping with the community standards of medical care. All concomitant medication will be recorded on the eCRF including all prescription, over-the-counter products, herbal supplements, and IV medications and fluids. If changes occur during the study period, documentation of drug dosage, frequency, route and date should also be included on the eCRF.

All concomitant medications received within 28 days before the first dose of study intervention and up to 30 days after the last dose of study intervention should be recorded. All concomitant medications administered during SAEs or ECIs are to be recorded. SAEs and ECIs are defined in Section 8.4.

Prohibited medications should not be used during the treatment phase of the study.

## 6.5.1 MK-1088 Supportive Care

Medications required to treat AEs or concurrent illnesses, other than those listed as prohibited, (Section 6.5), are allowed during the study. These include antiemetics, growth factors, and other supportive care medications. Contraceptive medications as described in Appendix 5 are allowed.

Any supportive care cancer treatment should not be CYP3A4 inhibitors/inducers (Table 6).

Every medication taken by the participant during the study and the reason for use must be recorded in the eCRF. Note that the use of any concomitant medication must relate to the documented medical history, prophylaxis, or an AE of the participant.

## 6.5.2 Rescue Medications and Supportive Care

No rescue or supportive medications are specified for use in this study.

## 6.5.3 Pembrolizumab Supportive Care

Participants should receive appropriate supportive care measures as deemed necessary by the treating investigator including, but not limited to, the items outlined below.

Suggested supportive care measures for the management of AEs with potential immunologic etiology are outlined along with the dose modification guidelines in Section 6.6.

## 6.6 Dose Modification (Escalation/Titration/Other)

#### 6.6.1 Dose Administration/Escalation

## **6.6.1.1 Dose Administration (Preparation)**

Details on preparation and administration of MK-1088 (and pembrolizumab) are provided in the appropriate Pharmacy/Procedures Manual.

## **6.6.2** Definition of Dose-limiting Toxicity

All toxicities will be graded using NCI CTCAE Version 5.0 based on the investigator assessment.

The DLT window of observation will be during Cycle 1.

The occurrence of any of the following toxicities during Cycle 1 will be considered a DLT, if assessed by the investigator to be possibly, probably, or definitely related to study intervention administration.

- Grade 4 nonhematologic toxicity (not laboratory).
- Grade 4 hematologic toxicity lasting ≥7 days, except thrombocytopenia:

Grade 4 thrombocytopenia of any duration

Grade 3 thrombocytopenia associated with clinically significant bleeding

• Any nonhematologic AE ≥Grade 3 in severity should be considered a DLT, with the following exceptions: Grade 3 fatigue lasting ≤3 days; Grade 3 diarrhea, nausea, or

vomiting without use of antiemetics or antidiarrheals per standard of care; Grade 3 rash without use of corticosteroids or anti-inflammatory agents per standard of care.

Any Grade 3 or Grade 4 nonhematologic laboratory value if:

Clinically significant medical intervention is required to treat the participant, or

The abnormality leads to hospitalization, or

The abnormality persists for >1 week

The abnormality results in a DILI (see Section 8.4.7 for criteria)

Exceptions: Clinically nonsignificant, treatable, or reversible laboratory abnormalities including liver function tests, uric acid, etc.

• Febrile neutropenia Grade 3 or Grade 4:

Grade 3 is defined as ANC  $<1000/\text{mm}^3$  with a single temperature of >38.3 degrees C (101 degrees F) or a sustained temperature of  $\ge 38$  degrees C (100.4 degrees F) for more than 1 hour.

Grade 4 is defined as ANC <1000/mm³ with a single temperature of >38.3 degrees C (101 degrees F) or a sustained temperature of ≥38 degrees C (100.4 degrees F) for more than 1 hour, with life-threatening consequences and urgent intervention indicated.

- Prolonged delay (>2 weeks) in initiating Cycle 2 due to intervention-related toxicity.
- Any intervention-related toxicity that causes the participant to discontinue intervention during Cycle 1.
- Missing >25% of MK-1088 doses as a result of drug-related AEs during the first cycle.
- Grade 5 toxicity.

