Participants will be initially enrolled to receive MK-1088 in monotherapy (Arm 1). Enrollment in Arm 1 (MK-1088 in monotherapy) at DL2 will begin once all participants complete Cycle 1 at DL1 of Arm 1 and a dose-escalation decision has been made. Enrollment in Arm 2 (MK-1088 in combination with pembrolizumab) at DL1 may begin after all participants complete Cycle 1 at DL1 of Arm 1 and a dose-escalation decision has been made. Thus, the starting dose of MK-1088 in the combination arm will be at least 1 level below the dose level being tested concurrently in the MK-1088 monotherapy arm. The final number of participants enrolled in Part 1 will depend on the empirical safety observations (DLT), and what dose is ultimately identified as the RP2D using the adjusted mTPI design.

Based on the adjusted mTPI design, it is anticipated that data from 14 participants at a dose level will provide sufficient data to declare an MTD or RP2D. However, should there be clinical PK or safety reasons, additional participants and/or dose levels may be evaluated. The pool-adjacent-violators algorithm [Ji Y, Li Y, Bekele BN 2007] will be used to estimate the DLT rates across doses in each treatment arm under the assumption of monotonicity between DLT rates and dose levels. The dose with an estimated DLT rate closest to 30% may be treated as a preliminary RP2D. The totality of the data will be considered before deciding on the dose(s) to carry forward to Part 2. The RP2D of MK-1088 in the combination arm (Arm 2) may equal, but will not exceed, the RP2D in the MK-1088 monotherapy arm (Arm 1).

In Part 2, safety and efficacy of MK-1088 in combination with pembrolizumab at the RP2D defined in Part 1 Arm 2 will be assessed. At least 3 indication-specific expansion cohorts are planned based on evolving data and will be incorporated into an amendment before initiating Part 2. Additional lower and/or higher doses of MK-1088 in combination with pembrolizumab may also be explored in Part 2. The final RP2D for future studies will be confirmed using all available safety information (including early and late toxicities from

PRODUCT: MK-1088
PROTOCOL/AMENDMENT NO.: 002-01

Parts 1 and 2), as well as PK and pharmacodynamic data, and preliminary efficacy assessments.

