A participant may not cross over from Arm 1 (monotherapy) into Arm 2 (combination therapy with pembrolizumab) until that participant has completed the DLT evaluation period (ie, 21 days) in Arm 1. Participants who are eligible for crossover from Arm 1 to Arm 2 will complete the Arm 2 screening phase to ensure eligibility. In participants who cross over to Arm 2, screening assessments obtained for Arm 1 may be eligible for crossover screening if the assessments were obtained within 28 days before Arm 2 treatment initiation; an additional tumor biopsy specimen is not required. These participants will continue to undergo

their scheduled activities. Participants may receive the highest dose of MK-1088 that has already shown safety and tolerability in combination with pembrolizumab (DLT evaluation period completed for that combination dose).

Participants who are eligible to receive combination treatment due to radiographically confirmed PD while in Arm 1, will not be included in the adjusted mTPI dose-escalation determination for Arm 2, as that specific dose level cohort must have already shown safety and tolerability. However, their data may be included retrospectively in determination of the RP2D for the combination treatment. These participants' safety and efficacy data will be analyzed separately from that of the participants enrolled in Arm 2. Once they discontinue from any part of the study, participants will be treated at the discretion of the physician.

Participants who cross over to combination treatment will be eligible to receive a maximum of 35 cycles of combination treatment irrespective of the number of cycles of MK-1088 received in monotherapy.

Participants who discontinued monotherapy in Arm 1 due to a DLT are not eligible for crossover to Arm 2.

Participants who discontinue treatment for reasons other than radiographic PD will have posttreatment follow-up for disease status (including imaging) until PD, initiating a new anticancer therapy, withdrawing consent for study participation, or becoming lost to follow-up.

After discontinuation of study therapy, each participant will be contacted by telephone every 12 weeks ( $84 \pm 7$  days) for survival until withdrawal of consent to participate in the study, becoming lost to follow-up, death, or end of the study, whichever occurs first.

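### Read literally, the laboratory exception in the DLT definition cancels its own triggers; separately, some DLT criteria can still be open at Day 21 with no rule to wait

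*Combined protocol and SAP*

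**What the plan says.** **Laboratory criterion.** Section 6.6.2 makes a Grade 3 or 4 nonhematologic laboratory value a DLT on any of four triggers: it needs clinically significant treatment, it leads to hospitalization, it lasts more than 1 week, or it results in a DILI as defined in Section 8.4.7. An exception follows. It covers values without clinical significance, but also values that can be treated or that reverse, and it names liver function tests among its examples. Nothing says which prevails.

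**Timing.** Section 6.6.2 states: "The DLT window of observation will be during Cycle 1". Section 4.1 gives the length when it bars crossover until the participant has "completed the DLT evaluation period (ie, 21 days) in Arm 1". The DLT list nevertheless includes "Prolonged delay (>2 weeks) in initiating Cycle 2 due to intervention-related toxicity", Grade 4 hematologic toxicity (other than thrombocytopenia) lasting at least 7 days, and the laboratory persistence trigger above. It also includes "Missing >25% of MK-1088 doses as a result of drug-related AEs during the first cycle".

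**Opening the next dose.** Under Section 4.1, Arm 1 DL2 opens "once all participants complete Cycle 1 at DL1 of Arm 1 and a dose-escalation decision has been made", and Arm 2 DL1 may open on the same conditions. Section 6.3.1 says: "Each new dose cohort will open for enrollment without delay once" two conditions are met, namely that "the 21-day DLT observation period of the previous dose cohort is completed and a dose-escalation decision is made".

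**The concern.** DLT counts are the only input to Table 3. A DLT definition has to let two investigators classify the same event alike, and each status has to be known, or explicitly handled, when the table is read. Section 6.6.2 falls short on the first count for laboratory values. Sections 4.3.1.3, 6.3.1 and 6.6.2 together fall short on the second for toxicity that starts late in Cycle 1.

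At stake is the escalation decision and the participants enrolled on it. One DLT left out can open the next dose when the complete count says stay. Section 4.3.1.2 allows steps of up to 100%, and the first two planned steps (100 to 200 mg and 200 to 400 mg) are doublings. At DL1 of Arm 1, a single decision opens two cohorts.

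**Working it through.** **1. Triggers against exception (Section 6.6.2).**
- *Needs significant treatment:* a value that responds to that treatment is treatable, so it is exempt.
- *Leads to hospitalization:* exempt if the value is corrected in hospital.
- *Lasts more than 1 week:* a value that normalizes after ten days has met the trigger, and has also reversed, so it is exempt.
- *Results in DILI:* Section 8.4.7 defines this by AST or ALT at least 3 × ULN with bilirubin at least 2 × ULN and alkaline phosphatase below 2 × ULN. These are liver function tests, which the exception names.

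On the literal wording each trigger can be cancelled. This needs no assumption about late onset.

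**2. Calendar.** Cycles last 21 days, so Cycle 1 ends on Day 21 and Cycle 2 is due on Day 22. A delay is exactly 14 days on Day 22 + 14 = 36 and exceeds 14 days from Day 37. The ±3-day visit window moves this to Day 34 (from Day 19) or Day 40 (from Day 25). Counting the onset day, Grade 4 hematologic toxicity starting on Days 16–21 cannot reach 7 days by Day 21. A laboratory value starting on Days 15–21 cannot exceed 7 days by then.

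**3. What the missed-dose criterion already catches.** For a hold lasting to Day 21:
- from Day 16: 6/21 = 28.6% missed, already a DLT;
- from Day 17: 5/21 = 23.8%, not a DLT by this route. At least 16/21 = 76.2% was taken, so the participant stays evaluable under the 75% rule of Section 5.5;
- from Day 18: 4/21 = 19.0%;
- hold first applied at Cycle 2 Day 1: 0/21.

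The gap is therefore limited to holds starting on Day 17 or later.

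**4. Two cases that remain.**
- The Day 15 visit may fall on Days 12–18. Grade 4 neutropenia first seen on Day 17 or 18 requires a hold (Table 7) and misses 5 or 4 doses. It reaches 7 days on Day 23 or 24 counting the onset day, or Day 24 or 25 in full days.
- Hematology is next scheduled at the Cycle 2 Day 1 predose check. Afebrile Grade 3 hematologic toxicity without bleeding, first found there, misses no Cycle 1 dose. Table 7 requires a hold once it exceeds 5 days. Only the delay criterion can then make it a DLT.

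**5. Effect on Table 3.** Lower the DLT count by one in every possible step for n = 3, 4, 5, 6 (3 + 4 + 5 + 6 = 18 steps):

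| Change | Steps | True counts |
|---|---|---|
| S to E | 4 | 1/3, 1/4, 1/5, 2/6 |
| D to S | 4 | 2/3, 2/4, 3/5, 3/6 |
| DU to D | 4 | 3/3, 3/4, 4/5, 4/6 |
| none | 6 | the rest |

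DU to D is a real change: Section 4.3.1.3 closes a DU dose to further study, while D leaves it available.

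**6. Probability.** The chance that a cohort's true count sits in an S-to-E cell at a 30% DLT rate is the binomial probability of 1 DLT for n = 3, 4, 5 and of 2 DLTs for n = 6: 44.1%, 41.2%, 36.0% and 32.4%. These are ceilings, to be multiplied by the chance that a DLT in that cohort is still pending. The documents do not give that chance. As an illustration, let q be the assumed share of DLTs pending and read as no DLT. For n = 3 the chance of reading 0/3 is (1 − 0.30(1 − q))³:

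| q | 0 | 2% | 5% | 10% | 20% |
|---|---|---|---|---|---|
| P(0/3) | 34.3% | 35.2% | 36.6% | 38.9% | 43.9% |

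**7. Length of a wait.** If the last-enrolled participant is on hold, 37 − 21 = 16 days. If it is the first-enrolled, the minimum 24-hour spacing puts that participant at Day 23 (n = 3) or Day 26 (n = 6) when the last reaches Day 21. The wait is then 37 − 23 = 14 or 37 − 26 = 11 days. With 14 days of accrual it is 37 − 35 = 2 days.

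**The case against.** **On the laboratory exception.** The triggers are probably meant to prevail, and a sensible investigator would apply them. Other criteria, such as discontinuation in Cycle 1, missed doses, or the general one for nonhematologic AEs of Grade 3 or more, may catch some of the same events. That stands in part. But if the general AE criterion decided laboratory values, the separate laboratory criterion would be redundant, so it does not settle precedence. A reader might infer that the plan intends to exempt DILI; the documents do not support that, since DILI is listed as a trigger.

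**On timing.** A reader might infer that the next dose opens automatically on Day 21. It does not: Sections 4.1 and 6.3.1 also require a decision, the study is open-label, Section 9.7 has data examined continuously, and Section 4.3.1.3 allows the schedule to be adjusted on emerging safety data. All of this stands. It permits waiting without requiring it, and does not say how to count a participant on hold.

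Table 3 counts evaluable participants, and Section 9.5.1 illustrates evaluability as having finished Cycle 1 without a DLT or having had one. An undetermined participant could be read as neither. With the minimum of 3 per dose, that reading would keep a cohort of 3 out of the table, but it does not fully protect cohorts of 4 to 6. Section 4.3.1.3 also caps added enrollment after a stay decision until more DLT data arrive, which limits D-to-S errors but not S-to-E errors.

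Finally, the cases are edge cases. In the second, whether toxicity first found at Cycle 2 Day 1 belongs to Cycle 1 is itself arguable. That is fair, and is a reason to state the rule.

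**Conclusion.** The main point is the laboratory exception. As written it can remove events that the triggers count, and the text sets no precedence. This is a defect in the definition of the primary endpoint.

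The second point holds in a limited form. The Cycle 2 delay criterion cannot be established by Day 21, and the two duration criteria may not be when onset is in the third week. Waiting is allowed but not required, and no text deals specifically with an unresolved case or directs that the decision be reviewed when a DLT is established later. The gap is narrow, because the missed-dose criterion already catches holds running from Day 16 or earlier to Day 21.

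One uncounted DLT changes the action in 12 of 18 steps for cohorts of 3 to 6. The 32–44% range should not be read as the chance of a wrong escalation: it is only the chance of sitting in an S-to-E cell at an assumed 30% rate. The chance of a pending DLT is unknown and probably low.

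Nor do the documents support inferring that late DLTs are lost for good. They may still enter the final DLT estimate, and the choice of RP2D rests on all the safety data. Day 37 assumes the nominal Day 22 start of Cycle 2.

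**What to change.** **Section 6.6.2, laboratory criterion.** Limit the exception to clinically nonsignificant values that meet none of the four triggers.

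**Section 6.6.2, timing.** State that the delay and duration criteria count when the toxicity began in Cycle 1 or delays Cycle 2, even if they are established after Day 21.

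**Sections 4.3.1.3 and 6.3.1.** Do not escalate from Table 3 while any DLT-evaluable participant has an unresolved intervention-related toxicity that could still meet a delay or duration criterion. Include toxicity found at the Cycle 2 Day 1 predose check, where that visit takes place. Count participants who stop after Cycle 1 without such a toxicity as they stand. Add any DLT established later to the Table 3 count and review the decision then in force.

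Pending cases should not be counted provisionally as DLTs. That could turn 1/3 into 2/3, which is D, and Section 4.3.1.3 stops the study for a D at the lowest dose.

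**Cost.** A few sentences in an amendment. The Cycle 2 Day 1 check is normally available by Day 22, and by Day 25 within the visit window. A longer wait arises only when a participant is on hold, and runs to about 16 days at most on the nominal calendar.
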